#### **8.2.4.3 Overall Survival**

Kaplan-Meier method will be used to estimate the overall survival rates at 1, 3 and 5 years among patients treated with combined Pembrolizumab, radiation therapy and +/- Cisplatin. 95% CI of these rates will be provided. These survival rates will be compared with historical data using the log-rank test. We will also use Cox model to compare the historical data if patient level data obtained from RTOG 9501.

#### **8.2.4.4 Biomarker Assessments**

All biomarker measures will be summarized with descriptive statistics, i.e., percentages for categorical outcomes and means/medians for continuous outcomes, with corresponding standard errors and 95% confidence intervals. Responses will be tabulated by determined response and toxicities will be tabulated by type and grade. For IHC, the percentage of positive cells per area will be multiplied by the staining intensity for each tumor to determine quantitative expression pre- and post-treatment; a 25% change in expression will be considered a positive response. We will use descriptive statistics and graphical displays to evaluate change in serum markers and flow cytometry markers between pre- and post-treatment.

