### 2.1 Trial Design

This study will be a two arm phase II trial including 80 patients with head and neck squamous cell carcinoma (HNSCC) eligible for resection. Patients who are identified to be clinically high risk (see inclusion) prior to resection will be screened and consented to receive 1 dose Pembrolizumab followed by resection. Post-resection, patients will be stratified and if high risk features are confirmed by pathology (extracapsular extension [ECE], or positive margins), patients will receive concurrent weekly Cisplatin, daily radiation and every three week Pembrolizumab as shown in schema. If those enrolled prior to resection are found to not have high risk pathological features, they will go on to receive radiation and Pembrolizumab. Eight patients from each group will be enrolled as part of a lead-in on a rolling basis to determine the safety of this combination with stopping rules if expected toxicity is exceeded. There will be a fair proportion of patients who are identified to be high risk prior to resection but do not have confirmed high risk pathologic features. Therefore, we expect that using our criteria, that at least 50% (or 40 patients) will have high risk features requiring chemotherapy in addition to radiation (CRT) and Pembrolizumab while the remaining intermediate risk patients will receive radiation and Pembrolizumab. For correlative studies, archived or fresh biopsy samples and resection tissue will be assessed by H&E and IHC for immune phenotype. Blood samples will also be collected as described in section 7 for correlative studies. Patients will be followed approximately weekly during treatment,

then monthly for the first 3 months following treatment and then every 3 months thereafter for the first two years. A repeat PET/CT or CT scan will be performed at 3 months post-treatment to assess for early relapse. Patients will be assessed every 3 months for the first 2 years and then every 6 months for the next 3 years for disease free survival (DFS) and overall survival (OS).

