### 3.2 Secondary Objectives & Hypotheses

**(1) Objective:** To estimate the 1 and 3 year overall survival (OS) combining Pembrolizumab with adjuvant CRT in patients with resected high risk HNSCC.

- **Hypothesis:** Combining Pembrolizumab to concurrent Cisplatin and radiation will increase OS in patients with resected HNSCC relative to historic data as there is not a current comparison in this trial.

**(2) Objective:** To estimate the 1 and 3 year overall survival (OS) combining Pembrolizumab with adjuvant radiation in patients with resected intermediate risk HNSCC.

- **Hypothesis:** Combining Pembrolizumab to radiation will increase OS in patients with resected HNSCC relative to historic data as there is not a current comparison in this trial.

**(3) Objective:** Determine the change in distribution of the tumor immune microenvironment before and after Pembrolizumab administration in tumor biopsy tissue using markers of T cells and T cell activation including but not limited to CD4, CD8, CD38, HLA-DR, PD-1 and PD-L1.

- **Hypothesis:** Pembrolizumab administration will result in enhanced immune stimulation in tumors marked by T cell infiltration/activation.

**(4) Objective:** Determine the baseline adenosine receptor expression in HNSCC patients and the effect of PD-1 inhibition by Pembrolizumab in activated T cells combined with peripheral T cell activation by flow cytometry.

- **Hypothesis:** Pembrolizumab administration will result in increased adenosine receptor expression which will confer resistance to T cell activation.

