### **7.1.3.2.2 Immunohistochemistry/Immunofluorescence/RNA In Situ Hybridization**

Archived biopsy and resected tissue and if fresh resected tissue (Cincinnati only) will be shipped to University of Cincinnati for analysis. FFPE and Frozen sections will be used to analyze the immune cell phenotype (markers include but are not limited to CD4, CD8, PD-1, FOXP3, A2aR, PD-L1, CD73).

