#### Secondary Endpoints

Overall Survival (OS): defined as the time from randomization to death due to any cause. Subjects without documented death at the time of the final analysis will be censored at the date of the last follow-up. OS at 1 and 3 years will be used as secondary endpoints.

Locoregional Control: failure was defined as the reappearance of tumor in the original tumor bed or the development of cervical-node metastases after treatment.

Biomarker analysis including proportion of T cell population subsets before and after immunotherapy both in tumor tissue and peripheral blood.

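### For T-cell lineage markers in tissue, the only IHC score and its 25% response rule multiply cell abundance by stain strength, so intensity alone can create or hide a response

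*Combined protocol and SAP*

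**What the plan says.** Objective (3) in section 3.2 is to "Determine the change in distribution of the tumor immune microenvironment before and after Pembrolizumab administration in tumor biopsy tissue using markers of T cells" and T-cell activation. Its listed markers include CD4, CD8, CD38, HLA-DR, PD-1 and PD-L1. The hypothesis is that "Pembrolizumab administration will result in enhanced immune stimulation in tumors marked by T cell infiltration/activation".

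Section 8.2.2 (Secondary Endpoints) gives the matching endpoint as "Biomarker analysis including proportion of T cell population subsets before and after immunotherapy both in tumor tissue and peripheral blood".

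Section 2.1 says that "archived or fresh biopsy samples and resection tissue will be assessed by H&E and IHC for immune phenotype". Section 7.1.3.2.2 adds that "FFPE and Frozen sections will be used to analyze the immune cell phenotype", with a non-exhaustive marker list that includes CD4, CD8, PD-1, FOXP3, A2aR, PD-L1 and CD73.

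Section 8.2.4.4 opens with a general commitment to summarise every biomarker measure descriptively, with standard errors and 95% confidence intervals. For IHC it then names a single scored quantity: "the percentage of positive cells per area will be multiplied by the staining intensity for each tumor to determine quantitative expression pre- and post-treatment". The response rule follows: "a 25% change in expression will be considered a positive response". The section gives no intensity scale, no direction for the 25%, and no distinction by type of marker.

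**The concern.** CD4, CD8 and FOXP3 are used here to say which T cells are present and how many. How darkly those cells stain is a different matter. A score that multiplies the two no longer tracks abundance, although the named endpoint is a proportion and the hypothesis is partly about infiltration.

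At stake is the response label. A tumor whose T-cell fraction has not moved can be labelled a responder because its stain is stronger. A tumor with a clear rise can be labelled unchanged because its stain is weaker. Section 4.2.3.3 presents the resection tissue taken after one pembrolizumab dose as a particular opportunity of this trial, so its main IHC readout should measure what the objective asks.

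**Working it through.** The plan gives no figure to reproduce on this point: no sample size, power or alpha attaches to the biomarker endpoint. The check is algebra on the score in section 8.2.4.4.

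**Inputs**
- P = percent positive cells and I = staining intensity, the two factors in section 8.2.4.4.
- The 25% rule, from the same section, read here as a relative increase (the text states neither relative nor direction).
- Assumption: an intensity scale of 1 to 3, because the documents give none. The P values below are also illustrations.

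**Formula**

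S = P × I, so S_post/S_pre = (P_post/P_pre) × (I_post/I_pre).

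The rule is met when this ratio is at least 1.25. If P is unchanged, the condition becomes I_post/I_pre ≥ 1.25. On any scale, therefore, a 25% rise in intensity alone is enough. This step needs no assumed values.

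**Illustrations**

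| Case | Score before | Score after | Change in P | Change in S |
|---|---|---|---|---|
| Rise hidden | 10 × 3 = 30 | 15 × 2 = 30 | +50% | 0% |
| Response created | 10 × 2 = 20 | 10 × 3 = 30 | 0% | +50% |
| Sign reversed | 30 × 2 = 60 | 24 × 3 = 72 | −20% | +20% |
| Threshold just met | 20 × 2 = 40 | 20 × 2.5 = 50 | 0% | +25% |

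The last row needs a scale, or an averaging method, that allows half-steps. With whole steps only, the smallest proportional rise is 2 to 3 (3/2 = 1.5), which already exceeds 1.25.

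**Proportion ratio needed to reach +25% on the score** = 1.25 ÷ (I_post/I_pre)

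| Intensity | Ratio | Proportion ratio needed |
|---|---|---|
| 1 to 3 | 3.00 | 0.417 |
| 1 to 2 | 2.00 | 0.625 |
| 2 to 3 | 1.50 | 0.833 |
| unchanged | 1.00 | 1.250 |
| 3 to 2 | 0.667 | 1.875 |
| 2 to 1 | 0.50 | 2.500 |
| 3 to 1 | 0.333 | 3.750 |

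For a one-step shift, the bar on the cell proportion runs from a fall of 37.5% (0.625) to a rise of 150% (2.5). If intensity can move two steps, it runs from 0.417 to 3.75.

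**After the change proposed below.** With the rule read on P alone, the first case is +50% and counts as a response, and the second is 0% and does not. No sample size or power figure in the plan changes.

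**The case against.** A reader might infer that the plan does not estimate its secondary biomarker endpoint at all. The documents do not support that. The opening sentence of section 8.2.4.4 covers every biomarker measure, and a T-cell subset proportion is one, so it can be reported under the plan as written. The product is introduced for the narrower purpose of quantifying expression. What stands is that no tissue proportion analysis is named, and that the only response rule is tied to the product.

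The endpoint is also wider than subset proportions. Section 8.2.2 says the biomarker analysis includes them, and objective (3) covers activation and checkpoint markers as well. For those an intensity-weighted score is defensible. The blood part is untouched, because section 8.2.4.4 handles flow cytometry and serum markers descriptively. The mismatch is confined to lineage markers in tissue IHC.

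A reader might also infer that intensity will differ between the two specimens for technical reasons, since pre-dose tissue may be archival, post-dose tissue is the resection, and both FFPE and frozen sections are used. That is possible but not shown. The documents contain no data on staining drift, section 7.1.3.2.2 sends the tissue to one institution, and section 7.1.2.7 asks sub-sites for the same FFPE formats for biopsy and resection. Weak staining could also push cells below the positivity cut-off, so percent positive is not immune.

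Finally, percent positive per area is not strictly a subset proportion. Its denominator is not defined as T cells, and the listed markers include no pan-T-cell marker. This objection stands and shapes the remedy.

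**Conclusion.** The point holds in a limited form. For CD4, CD8 and FOXP3 in tissue, the single IHC score and the 25% rule combine abundance with stain strength, so the rule can mislabel a change in T-cell abundance in either direction. That follows from the formula on any intensity scale. The specific sizes, such as a required proportion ratio of 0.625 when intensity goes from 1 to 2 or 3.75 when it goes from 3 to 1, rest on the assumed 1–3 scale and on reading the rule as a relative increase.

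How often this would happen is unknown. The consequence is modest: the biomarker analysis is descriptive and secondary, with no test or alpha attached, and percent positive must already be scored to form the product. It is a worthwhile clarification and has no bearing on the efficacy or safety conclusions.

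**What to change.** Amend section 8.2.4.4 as follows:
- For T-cell lineage markers in tissue (CD4, CD8, FOXP3), base the pre/post comparison and the 25% rule on percent positive cells, and state the denominator.
- Where the markers allow, add a subset proportion or ratio, such as CD8 to CD4 or CD8 to FOXP3. The background in section 4.1.1 already cites the CD8-to-FOXP3 ratio as prognostic.
- Keep the percent-times-intensity score for expression and checkpoint markers such as PD-L1 and A2aR.
- Tabulate both components for every marker.
- State the intensity scale and the direction of the 25% change.

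The cost is SAP wording and one more column per marker. No new assay is needed, because both components are already scored. Percent positive would remain sensitive to tissue cellularity and to the positivity cut-off, and the SAP should say so.

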### **9.0 LABELING, PACKAGING, STORAGE AND RETURN OF CLINICAL SUPPLIES**

#### **9.1 Investigational Product**

The investigator shall take responsibility for and shall take all steps to maintain appropriate records and ensure appropriate supply, storage, handling, distribution and usage of investigational product in accordance with the protocol and any applicable laws and regulations.

Clinical Supplies will be provided by Merck as summarized in Table 7.

Table 7 Product Descriptions

Product Name & Potency	Dosage Form
Pembrolizumab 50 mg	Lyophilized Powder for Injection
Pembrolizumab 100 mg/ 4mL	Solution for Injection
Cisplatin 10mg	Lyophilized Powder for Injection

The Cisplatin will be supplied by commercially available product.

#### **9.2 Packaging and Labeling Information**

Clinical supplies will be affixed with a clinical label in accordance with regulatory requirements.

### **9.3 Clinical Supplies Disclosure**

This trial is open-label; therefore, the subject, the trial site personnel, the Sponsor and/or designee are not blinded to treatment. Drug identity (name, strength) is included in the label text; random code/disclosure envelopes or lists are not provided.

### **9.4 Storage and Handling Requirements**

Clinical supplies must be stored in a secure, limited-access location under the storage conditions specified on the label.

Receipt and dispensing of trial medication must be recorded by an authorized person at the trial site.

Clinical supplies may not be used for any purpose other than that stated in the protocol.

### **9.5 Returns and Reconciliation**

The investigator is responsible for keeping accurate records of the clinical supplies received from Merck or designee, the amount dispensed to and returned by the investigational pharmacy (if used per site) and the amount remaining at the conclusion of the trial.

Upon completion or termination of the study, all unused and/or partially used investigational product will be destroyed at the site per institutional policy. It is the Investigator's responsibility to arrange for disposal of all empty containers, provided that procedures for proper disposal have been established according to applicable federal, state, local and institutional guidelines and procedures, and provided that appropriate records of disposal are kept.

## **10.2 Compliance with Financial Disclosure Requirements**

Financial Disclosure requirements are outlined in the US Food and Drug Administration Regulations, Financial Disclosure by Clinical Investigators (21 CFR Part 54). It is the Sponsor's responsibility to determine, based on these regulations, whether a request for Financial

Disclosure information is required. It is the investigator's/sub-investigator's responsibility to comply with any such request.

### **10.3 Compliance with Law, Audit and Debarment**

By signing this protocol, the investigator agrees to conduct the trial in an efficient and diligent manner and in conformance with this protocol; generally accepted standards of Good Clinical Practice (e.g., International Conference on Harmonization of Technical Requirements for Registration of Pharmaceuticals for Human Use Good Clinical Practice: Consolidated Guideline and other generally accepted standards of good clinical practice); and all applicable federal, state and local laws, rules and regulations relating to the conduct of the clinical trial.

### **10.4 Compliance with Trial Registration and Results Posting Requirements**

Under the terms of the Food and Drug Administration Modernization Act (FDAMA) and the Food and Drug Administration Amendments Act (FDAAA), the Sponsor of the trial is solely responsible for determining whether the trial and its results are subject to the requirements for submission to the Clinical Trials Data Bank, <http://www.clinicaltrials.gov>. Information posted will allow subjects to identify potentially appropriate trials for their disease conditions and pursue participation by calling a central contact number for further information on appropriate trial locations and trial site contact information.

### **10.5 Quality Management System**

By signing this protocol, the Sponsor agrees to be responsible for implementing and maintaining a quality management system with written development procedures and functional area standard operating procedures (SOPs) to ensure that trials are conducted and data are generated, documented, and reported in compliance with the protocol, accepted standards of Good Clinical Practice, and all applicable federal, state, and local laws, rules and regulations relating to the conduct of the clinical trial.

### **10.6 Data Management**

#### **10.6.1 Data Storage**

Data collection and storage will be managed by the University of Cincinnati Cancer Center, Clinical Trials Office (UCCC CTO). The UCCC CTO will maintain storage of all clinical data in accordance with federal guidelines and GCP. Data will be entered in a secure, password protected storage database, OnCore and/or RedCap. All hardcopies of data will be securely maintained (in a locked room or cabinet) and will only be accessible to members of the study team.

### **10.6.2 Data and Safety Monitoring**

Adverse event lists, guidelines, and instructions for AE reporting can be found in Section 7.0 (Adverse Events: List and Reporting Requirements).

Any new significant finding that may affect the patient's willingness to continue in the study will be shared with patients. Immediately after the study is approved and before the first patient is enrolled, investigators will meet, develop and finalize all measurements/variables for the study. Each patient, once enrolled, will be provided a unique ID for the study. Personal information, such as name, SSN, address, phone number and DOB, will be de-identified. Confidentiality will be maintained during the phases of the trial including monitoring, preparation of interim results, review, and response to monitoring recommendations. Exceptions may be made under circumstances where there are serious adverse events or when it is deemed appropriate for patient safety.

Study progress will be monitored regularly by the UCCC Data Safety Monitoring Board (DSMB). Membership consists of persons independent of, and without any conflicts of interest with, this trial. The DSMB includes experts in the fields of relevant clinical expertise (oncology) and biostatistics.

It is the responsibility of the sponsor-investigator to ensure that the DSMB is apprised of all new safety information relevant to the study IND and the study. Study progress & safety information will be prepared by the DSMB Coordinator with input from the PI as to the current status of the trial. This compiled information presented to the DSMB will include: a narrative summary from the PI as to trial progress and identification of any trends of significance or explanation of any SAEs or other safety related events; the accrual rate with projected completion date for the accrual phase; exclusion rates and reasons; pretreatment characteristics of patients accrued when relevant; and, the frequency and severity of adverse events.

The DSMB will function in an advisory capacity and recommendations/requests from the DSMB will be reviewed by the sponsor-investigator and promptly addressed.

The study data from participating sub-sites will be reviewed remotely via RedCAP and in person by the Study Monitor as per the Clinical Monitoring Plan (Plan kept on file with UCCC CTO office).

## **11.0 APPENDICES**

### **11.1 ECOG Performance Status**

Grade	Description
0	Normal activity. Fully active, able to carry on all pre-disease performance without restriction.
1	Symptoms, but ambulatory. Restricted in physically strenuous activity, but ambulatory and able to carry out work of a light or sedentary nature (e.g., light housework, office work).
2	In bed <50% of the time. Ambulatory and capable of all self-care, but unable to carry out any work activities. Up and about more than 50% of waking hours.
3	In bed >50% of the time. Capable of only limited self-care, confined to bed or chair more than 50% of waking hours.
4	100% bedridden. Completely disabled. Cannot carry on any self-care. Totally confined to bed or chair.
5	Dead.

\*As published in Am. J. Clin. Oncol.: *Oken, M.M., Creech, R.H., Tormey, D.C., Horton, J., Davis, T.E., McFadden, E.T., Carbone, P.P.: Toxicity And Response Criteria Of The Eastern Cooperative Oncology Group. Am J Clin Oncol 5:649-655, 1982.* The Eastern Cooperative Oncology Group, Robert Comis M.D., Group Chair.

## 11.2 Common Terminology Criteria for Adverse Events V4.0 (CTCAE)

The descriptions and grading scales found in the revised NCI common terminology criteria for adverse events (CTCAE) version 4.0 will be utilized for adverse event reporting. (<http://ctep.cancer.gov/reporting/ctc.html>)

